Women attending the reference hospital due to cervical shortening in twin pregnancies and fulfil the entry criteria (dichorionic twin pregnancy with cervical shortening \leq 25th percentile and do not fulfil the exclusion criteria), the study will be proposed. The patients will be informed of the intended therapeutic effect and possible side effects. If they agree and after obtaining their informed consent, they will be randomised according to the respective gestational week to either usual management (=control group) or cervical pessary placement up to 37 weeks (=pessary group). According to the gestational week and when the cervical shortening is under the 25th percentile the patients will be randomized to the following subgroups: gestational age in weeks 16-20, gestational age in weeks 20-24 and gestational age in weeks 24-28.

Specifically, the 25th centile of cervical length is defined at 32 mm, 30 mm and 28 mm for the 16+0 – 19+6, 20+0 – 23+6 and 24+0 – 28+0 weeks of gestation respectively.

2.3. Name and description of the device under investigation.

The Arabin cervical pessary, which is CE-certified for preventing SPB (CE 0482 / EN ISO 13485: 2012 + AC:2012 annex III of the council directive 93/42 EEC).

See annex I.

2.4. Statement that testing will be performed according to protocol, GCP and applicable legal requirements.

The Clinical Trial will be conducted following the protocol, the GCP, and all legal requirements.

3. Objective

This study aims to investigate the benefit of placing a cervical pessary in comparison to the expectant standard management in dichorionic twin pregnancies with cervical shortening \leq 25 percentile in terms of long-term survival without neurodevelopmental disability of the children.

Hereby, a standardized validated test called 'Ages and Stages 3rd edition' should evaluate the children's neurodevelopment at the age of 3 years. The test can be conducted by the parents and takes approximately 12 minutes. The questionnaires will be provided by the sponsor.

4. Design

4.1. Specific description of primary and secondary variables.

4.1.1. Primary outcome:

- Children`s survival without neurodevelopmental disability at the age of 3.

4.1.2. Secondary outcomes:

[figure not shown]
- Offspring
 - Time to birth
 - Preterm birth before 37 weeks: rate of delivery before 36+6 weeks
 - Preterm birth before 34 weeks: rate of delivery before 33+6 weeks
 - Preterm birth before 32 weeks: rate of delivery before 31+6 weeks

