 - Preterm birth before 30 weeks: rate of delivery before 29+6 weeks
 - Preterm birth before 28 weeks: rate of delivery before 27+6 weeks
 - Birth weight: median weight (g) of the newborns at birth
 - Fetal or neonatal death: rate of intrauterine demise or neonatal death during the first 24 hours
 - Neonatal morbidity: rate of major adverse neonatal outcomes before discharge from the hospital
 - Intraventricular Haemorrhage (IVH): grades III-IV
 - Retinopathy of prematurity
 - Respiratory Distress Syndrome (RDS): grades II-IV,
 - Need for ventilation > 72 h
 - Necrotising enterocolitis
 - Proven or suspected sepsis, antibiotics (>5 days)
 - Need (Duration in days) for neonatal special care (NICU)
 - Harm from intervention
- Mother:
 - Maternal death
 - Significant maternal adverse events (rate):
 - Heavy bleeding: bleeding that requires a medical intervention
 - Cervical tear: cervical rupture due to the pessary placement
 - Uterine rupture: rupture of the uterus due to contractions or surgery
 - Physical or psychological intolerance to pessary: discomfort or pain due to the pessary that makes daily life uncomfortable (number of cases)
 - Rupture of membranes before 32 weeks: rate of–rupture of amniotic membranes before 31+6 weeks

[figure not shown]
- Infection/inflammation
- Hospitalisation for threatened preterm labour before 32 weeks: requirement of hospitalisation due to preterm contractions that need medical treatment to try to stop them before 31+6 weeks (rate)
 - Mean hospital stay duration: number of days of admittance at the hospital
 - Use of tocolytic treatment: Type of tocolytic, days of treatment, dose

4.2. Description of the trial design.

Open Multicentre International Collaborative Randomized Controlled Trial, in parallel groups, based on intention-to-treat analysis comparing the placement of a prophylactic cervical pessary with usual management in twin pregnancies with shortened cervix ≤ 25 percentile

4.3. Flowchart.

4.4. Description of the medical device and the treatment regimen.

The cervical pessary is a vaginal device (silicone ring) that is used to treat pregnant women for preventing spontaneous preterm birth. This device can be easily placed around the uterine cervix without pain (see annex I).

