The pessary will be inserted during a preventive examination in pregnancy in the examination room. This procedure does not need anaesthesia and it does not need to be done in a surgery room. After the insertion of the pessary the correct fit of the pessary is verified by transvaginal ultrasound and in case it does not fit perfectly, it can easily be adjusted. The pessary will be removed at 37+0 weeks of gestation, or before if any unexpected event occurs (see 4.6).

After insertion of the pessary the obstetrical management during the pregnancy will be the same in both groups. Further surveillance of the pregnancy will not be influenced by the participation on the study.

7. Efficacy assessment

7.1. Specification of efficacy parameters: Primary and secondary endpoints.

This study aims to investigate the benefit of placing a prophylactic cervical pessary in comparison to the usual management in twin pregnancies with cervical shortening ≤ 25 percentile in terms of long-term survival without neurodevelopmental disability of the children.

7.2. Methods and timing to assess records and analyze the efficacy parameters.

The patients will be assessed according to usual management in a twin pregnancy.

	Regular preventive exam	Regular preventive exam	Postnatal evaluation	3 years follow up (corrected age)
Study procedure	study inclusion			
Informed consent	x			

Randomisation	x			
Pessary placement	x			
Pessary removal		x at 37 WoG		
physical exams				
Abdominal US	x	x		
Vaginal US	x Cervical length ≤ 25 percentile			
pH-Value	pH < 4,4			
Neonatal Examination			x	
Ages and stages test				x
Exam at paediatrician				x

8. Assessment of Safety

8.1. Procedures to record and report adverse events.

If a serious and unexpected adverse effect occurs during pessary treatment, it will be notified to the study Sponsor. The Department of Obstetrics and Gynecology of the Sponsor will fill the side effects document to notify it to the *Landesärztekammer Hessen*.

The patient affected by the adverse effect will be followed more intensively during the first days and if nothing else occurs, she will return to the standard control.

8.2. Definitions.

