A medically qualified investigator will assess the relationship of AEs to the study medication.

All SAEs must be reported to the main investigator. He will perform an initial check of the report, request any additional information, and he will notify it to the Ethics Committee. All SAE information will be recorded. It may be appropriate that some SAEs do not require immediate reporting but this must be justified. Justification might be determined, for example, by admission to hospital, or prolongation of hospitalization, where this is to be expected in the underlying disease or condition.

All adverse events (AE) life-threatening or resulting in death will be notified within 24 hours. All AE that are not life-threatening will be notified within 15 days. The rest of AE will be recorded and analyzed at the end of the study.

9. Statistics

9.1. Description of statistical methods.

The primary statistical aim is to compare the primary combined outcome “long-term survival without neuro-developmental disability at 3 years follow up” with a two-sided Cochran-Mantel-Haenszel-Test and a significance level of $\alpha=0.05$. The primary outcome refers to a combined event in any of the twin and will be analysed for all pregnancies with available primary endpoint. The stratified study design is accounted by this stratified test according to the gestation groups.

The main statistical evaluation will be performed at two time points. (1) The complete data set for the secondary endpoints will be available after the last women enrolled in this study has delivered her twins, so the analysis of these outcome parameter will be done right after this event. (2) The primary outcome will be evaluated 3 years after the last woman enrolled in this study has delivered her twins.

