Neonatal Morbidity	Cochran-Mantel-Haenszel-Test, Chi-Quadrat Test
Need for Hospitalization (mother)	Cochran-Mantel-Haenszel-Test, Chi-Quadrat Test
Days of Hospitalization (mother)	van Elteren Test, Wilcoxon-Mann-Whitney Test
Maternal Adverse Events	Cochran-Mantel-Haenszel-Test, Chi-Quadrat Test
Pessary Intolerance	Cochran-Mantel-Haenszel-Test, Chi-Quadrat Test
Vaginal Infections	Cochran-Mantel-Haenszel-Test, Chi-Quadrat Test

9.2. Expected number of subjects to be included.

For sample size calculation, we account for the stratified design and assume three equally large gestation groups. For the pessary group, we assume a combined event rate of at least 8% for the primary outcome and for the comparison of the pessary group with the control group we assume an odds ratio of 2.29. This odds ratio correspond to the lower bound of a one-sided confidence interval for the event rate given in van't Hooft (ProTwin Trial¹²). To reach a power of at least 80%, we have to evaluate at least 500 patients, 250 in the pessary group and 250 in the control group. To account for a drop out rate of 25%, overall n=672 pregnant women will be recruited.

9.3. Criteria for termination of the trial.

A non-justified case of maternal death (temporary stop until complete evaluation of the case by an external committee).

9.4. Selection of subjects to be included in each analysis.

The analysis will include all the subjects that have been randomised.

10. Direct Access to Data Source

Direct access will be granted to the authorized monitor, host institution and the regulatory authorities to permit trial-related monitoring, audits and inspections.

11. Quality and Control Assurance

Main investigator and collaborators: In order to ensure the Quality of the data they will provide instructions and training to the sites involved in the trial; review the CRF data; and detail of any other steps taken to ensure quality of research.

The main investigator will sign the study protocol and the “investigator’s commitment; he will apply for the Ethics Committee and the Director’s approval; and he will review the final report of the study.

The collaborators will assess patient’s eligibility, they will inform the patients and ask for the informed consent; and they will be responsible of the CRF and obtaining and registering all data.

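### The disability part of the primary outcome may be reported by parents who know the allocation, and no masking or check on differential reporting is planned, although a paediatrician exam is scheduled at the same 3-year point.

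*Combined protocol and SAP*

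**What the plan says.** Section 4.2 describes an "Open Multicentre International Collaborative Randomized Controlled Trial", and the synopsis calls it open-label. Mothers therefore know whether they had a pessary. Section 2.2 adds that they are told what the device is intended to achieve.

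The primary outcome (4.1.1) is survival of the children without neurodevelopmental disability at age 3. Section 3 names one instrument for the disability part, the ASQ-3, and says: "The test can be conducted by the parents and takes approximately 12 minutes". It names no other assessor and gives no score cut-off.

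The schedule in 7.2 marks two items in the 3-year column: the ASQ-3 and "Exam at paediatrician". Section 4.9 ends the study after a 3-year examination of the surviving children for neurodevelopmental disability. No section says what the exam contains, who performs it, whether that person knows the arm, or how its result bears on the endpoint.

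Section 9.1 compares the arms "with a two-sided Cochran-Mantel-Haenszel-Test and a significance level of" 0.05, stratified by gestation group. The event is counted per pregnancy if either twin has it. Sections 9.1 to 9.4 contain no rule for combining questionnaire and exam, and no sensitivity analysis for parent reporting.

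**The concern.** The primary outcome combines death, which parents cannot misreport, with disability, which may come from people who know the allocation and the hoped-for benefit. If parents in the two arms answer the same questionnaire differently for similar children, the difference enters the primary odds ratio as though it were a treatment effect. It could create an apparent benefit or hide a real one.

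Open-label treatment is unavoidable with a pessary, but unmasked assessment three years later is not, because the child carries no sign of the device. The schedule already contains a second assessment that could show whether the result depends on who reported it, yet nothing in the plan uses it that way.

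Death does not serve as a fallback check. The separate fetal or neonatal death outcome in 4.1.2 stops at 24 hours after birth, so later deaths appear only inside the composite.

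**Working it through.** **1. Inputs from section 9.2**

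- Pessary arm: "For the pessary group, we assume a combined event rate of at least 8% for the primary outcome".
- Effect: "for the comparison of the pessary group with the control group we assume an odds ratio of 2.29".
- Size: "250 in the pessary group and 250 in the control group", for at least 80% power at a two-sided 5% level.

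Implied control rate: odds = 2.29 × 0.08/0.92 = 0.1991, so the rate is 0.1991/1.1991 = 0.166. The design difference is 16.6% − 8.0% = 8.6 points.

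**2. The plan's own sample size**

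Pooled two-proportion formula, with mean rate 0.123:

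n = [1.96 × √(2 × 0.123 × 0.877) + 0.842 × √(0.08 × 0.92 + 0.166 × 0.834)]² / 0.0861² ≈ 228 per arm.

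With continuity correction: n/4 × [1 + √(1 + 4/(n × 0.0861))]² ≈ 251 per arm, against 250 stated. A simulated Cochran-Mantel-Haenszel test with three strata and 250 per arm gives power 0.80 with the correction and 0.84 without. The stated figure therefore reproduces with a continuity correction, and both versions of the test are shown below.

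**3. Illustration of differential reporting (assumed, not from the documents)**

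There is no true effect. Both arms have true event rate b, and control parents flag an extra share e of unaffected pregnancies:

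observed control rate c = b + (1 − b) × e; odds ratio = [c/(1 − c)] / [b/(1 − b)].

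The rejection probability is the exact binomial probability that the two-sided 5% two-proportion test rejects at 250 per arm.

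| b | e | c | Shift (points) | Odds ratio | Rejects, uncorrected | Rejects, corrected |
|---|---|---|---|---|---|---|
| 8% | 0 | 8.0% | 0 | 1.00 | 5% | 3% |
| 8% | 2% | 9.8% | 1.8 | 1.26 | 11% | 8% |
| 8% | 3% | 10.8% | 2.8 | 1.39 | 18% | 14% |
| 8% | 5% | 12.6% | 4.6 | 1.66 | 39% | 34% |
| 16.6% | 0 | 16.6% | 0 | 1.00 | 5% | 4% |
| 16.6% | 2% | 18.3% | 1.7 | 1.12 | 8% | 6% |
| 16.6% | 3% | 19.1% | 2.5 | 1.19 | 11% | 9% |
| 16.6% | 5% | 20.8% | 4.2 | 1.32 | 22% | 19% |

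One cell by hand (b = 8%, e = 5%, uncorrected): c = 0.08 + 0.92 × 0.05 = 0.126 and the pooled rate is 0.103. The standard error is √(2 × 0.103 × 0.897/250) = 0.0272 under the null and √((0.08 × 0.92 + 0.126 × 0.874)/250) = 0.0271 under the shifted rates. Then (0.046 − 1.96 × 0.0272)/0.0271 ≈ −0.27, and Φ(−0.27) ≈ 0.39.

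**4. Check with the planned test**

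The uncorrected Cochran-Mantel-Haenszel test was simulated with three strata and a reporting gap split evenly around the true rate. At an average rate of 12.5%, gaps of 2, 3, 4 and 5 points give false-positive rates of 10, 17, 27 and 39%. A 4-point gap gives 38% at an average rate of 8% and 22% at 16.6%. The pattern is the same.

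For scale, the largest shift in the table, 4.6 points, is 4.6/8.6 = 53% of the design difference.

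**The case against.** The strongest reply is that the plan never says parent report alone decides disability. The wording in section 3 is permissive, section 7.2 schedules a paediatrician exam, and section 4.9 suggests that the 3-year examination is meant to assess neurodevelopment. A reader might infer that the sponsor chose to rely on parents and to leave the exam out. The documents do not support that; they leave open which source decides and how the two combine. This part of the reply stands, and it is why the point concerns an unstated role and an unplanned check.

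A second reply is that using the exam is not free. Its content, examiner and data capture are undefined, centres lie in several countries, and section 14 says the study has no funding. That also stands. The exam can serve as a check only once a recorded result is defined.

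A third is that the bias is hypothetical. Its size and direction are assumed, the 39% comes from the largest assumed bias at the lowest base rate, and a 2% bias at 16.6% moves the corrected test only from about 4% to 6%. This is fair as to size. It does not remove the point, because the plan contains no analysis that would show whether the bias is small or large.

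**Conclusion.** The point holds as a recommended improvement. The design and sample size stand. In an open-label trial, the only instrument named for the disability component may be completed by parents who know the allocation. The plan masks no assessor and plans no comparison with the paediatrician exam scheduled for the same time.

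The illustrated false-positive rates run from 8 to 39% uncorrected and from 6 to 34% corrected, against 5% and 3 to 4% without bias. They assume no true effect, 250 evaluable pregnancies per arm, event rates of 8% or 16.6%, and 2 to 5% extra flagging by control parents. They are not an estimate of this trial's error rate.

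A reader might also infer that reporting bias could never be checked here. The documents do not support that: the exam is scheduled, so a check is possible if its result is recorded. The defect is that none is planned. The concern applies to disability only, not to death.

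**What to change.** Keep the ASQ-3 as the primary disability measure and make these changes before any 3-year data are examined by arm:

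- **Sections 3 and 4.1.1:** state the ASQ-3 cut-off that defines disability.
- **Section 7.2:** state that the 3-year paediatrician is not told the allocation and enters a simple coded disability result in the eCRF before seeing the ASQ-3. Define what that code means, so that centres record the same thing.
- **Scoring:** score the ASQ-3 forms without the arm label.
- **Section 9.1:** pre-specify a sensitivity analysis that repeats the stratified primary comparison with the paediatrician's result in place of the parent-reported disability component. Report agreement between the two sources by arm.
- **Section 9.1:** report death up to 3 years separately from disability.

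The cost is protocol and SAP wording, one eCRF item, an instruction to examiners and one extra analysis. No visit is added beyond the schedule. The downsides are some variation in the exam between centres and imperfect masking, because parents may reveal the arm. The sensitivity analysis would therefore reduce or expose reporting bias, but not rule it out.

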In a prospective randomised trial the "ProTwin Trial"⁸ 813 women with twin pregnancies at a gestational age of 16 weeks to 20 weeks were randomised to either

pessary treatment or expectant management. Subgroup analysis of women with a shortened cervix below the 25 percentile (=38 mm) showed for the pessary group a significant 6-fold decrease in perinatal mortality and a reduction of severe morbidity. This demonstrates that an early screening followed by an early intervention is essential for patients at-risk. A secondary analysis “*per protocol*” of the ProTwinTrial revealed that the success of pessary treatment was mostly dependent on the correct placement and the duration of the therapy ⁹.

A further prospective-randomised trial by Goya et. al ¹⁰ also proved a significant reduction of the preterm delivery rate in twin pregnancies with cervical shortening (<25 mm, 20-24 weeks of gestation) after placement of a pessary compared to expectant management; the reduction in mortality was less pronounced than in the ProTwin Trial. A new case-control-trial by Fox et al. ¹¹ showed a decrease in early preterm birth before 32 weeks of gestation (4.8% vs. 28.6%, P=.05), a considerable prolongation of pregnancy (65.2 d. vs. 52.1 d, P=.025) and a reduced neonatal morbidity (9.5% vs. 34.9%, P=.04) in twin pregnancies after pessary therapy.

A secondary analysis of the ProTwin Trial indicated a higher survival rate without neurodevelopmental disability in the long-term outcome 3 years after pessary treatment (92.4 vs. 73.8%, p=0.006) compared to expectant management ¹².

A prospective, randomised controlled trial by Nikolaides ¹³ and a cohort study by Monfrance ¹⁴ in twin pregnancies with short cervix showed no significant effect of the pessary therapy compared to expectant management.

Up to now there is just one Cochrane review available concerning pessary therapy and the authors concluded that in spite of the positive effects seen that more trials should be conducted ¹⁵.

2.2. Description of the study population.

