A descriptive analysis by preterm birth will be carried out calculating means and medians for quantitative variables and proportions with 95% confidence intervals for categorical variables. In general, statistical comparisons with the pessary arm and the control arms or other group comparisons for primary and secondary outcomes will be performed with stratified tests as well as comparisons in the gestation subgroups. Events will be analysed for each twin and for single children assuming appropriate random effect regression models. Further subgroup analyses regarding the cervical length will be performed (e.g. CL 15 to 25mm and below 15mm). All tests, see also examples in the synopsis, will be two-sided using a significance level of $\alpha=0.05$.

For the primary endpoint we expect to have a drop out rate of up to 25% due to the long follow-up time (3 years) of the study; but we do not expect to have lost data for the secondary endpoints because for these parameters the study has a short follow-up time till time to birth only.

An interim analysis shall be conducted on key safety parameters after birth of 300 twins: the following safety endpoints will be assessed by a one-sided test with $\alpha=1\%$

- on level of the neonates: rate of preterm birth, time to birth, birth weight, death, neonatal morbidity, harm of intervention
- and on the maternal level: rate of hospitalisation for threatened preterm labour < 32 weeks, rate of PRoM <32 weeks, rate of infection / inflammation, rate of physical or psychological intolerance to pessary, rate of SAR/SAE, death.

The trial will be terminated as negative if a disadvantage for the pessary-treatment can be found in one of these tests. To guarantee a high safety level the significance level is chosen more conservatively than in a Bonferroni correction.

All analysis will be carried out with SPSS® version 19.0 or later (IBM Company SPSS Inc. Headquarters, Chicago, Illinois, USA) and R version 3.2.3 or later (R Foundation for Statistical Computing, Vienna, Austria).

Primary Outcome	Statistical Test
Children`s Long-Term Survival without Neuro-developmental Disability (3-Years-follow up)	Cochran-Mantel-Haenszel-Test, using 3 strata according to WoG
Secondary Outcome	Statistical Test
Birth before 34 Weeks of Gestation	Cochran-Mantel-Haenszel-Test, Chi-Quadrat Test
Time to Birth	Cox-Regression
Birthweight	van Elteren Test, Wilcoxon-Mann-Whitney Test
Fetal / Neonatal Death	Cochran-Mantel-Haenszel-Test, Chi-Quadrat Test

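### The only offspring mortality outcome stops 24 hours after birth, so no separate comparison of later deaths is planned before the 3-year composite, and the interim death test probably uses the same cut-off

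*Combined protocol and SAP*

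**What the plan says.** Three parts of the plan bear on this.

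- **Secondary outcomes (4.1.2).** Mortality is "Fetal or neonatal death: rate of intrauterine demise or neonatal death during the first 24 hours". The next item is "Neonatal morbidity: rate of major adverse neonatal outcomes before discharge from the hospital". Its listed components are conditions such as severe intraventricular haemorrhage, necrotising enterocolitis, sepsis and prolonged ventilation. Death is not one of them.
- **Interim analysis (9.1).** "An interim analysis shall be conducted on key safety parameters after birth of 300 twins". Each endpoint on two lists is tested one-sided at the 1% level. The neonatal list reads "on level of the neonates: rate of preterm birth, time to birth, birth weight, death, neonatal morbidity, harm of intervention". The serious-event item, "rate of SAR/SAE, death", is in the maternal list. The consequence is binding: "The trial will be terminated as negative if a disadvantage for the pessary-treatment can be found in one of these tests".
- **Timing (9.1).** Secondary endpoints are analysed directly after the last delivery, and their follow-up is described as ending at birth. The primary outcome is evaluated 3 years after the last delivery, as a combined event in either twin, among pregnancies with the endpoint available.

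The rationale in 2.1 rests partly on a subgroup result from an earlier trial: "a significant 6-fold decrease in perinatal mortality and a reduction of severe morbidity".

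**The concern.** The trial's objective is survival without disability, and a mortality difference is part of its rationale. The intervention is meant to act through prematurity. Several complications that the plan itself lists, such as sepsis and necrotising enterocolitis, can lead to death after the first day. A twin who dies on day 2 or later is a non-event in the only mortality outcome reported before the 3-year analysis.

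Two results are at stake. The secondary mortality comparison could look neutral, or favour either arm, while deaths before discharge point elsewhere. And the interim death test, if it uses the same definition, runs on fewer events than it could have.

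**Working it through.** **1. Is there another early comparison of later deaths?**

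| Possible route | What the plan provides |
|---|---|
| Neonatal morbidity to discharge (4.1.2) | Death is not a listed component |
| Test table (9.1) | Names fetal/neonatal death, gives no other window |
| Interim serious events and death (9.1) | Maternal level |
| Notification of fatal events within 24 hours (8.3) | Case reporting, not a comparison of arms |
| Termination criterion (9.3) | Maternal death only |
| Primary outcome (9.1) | 3 years later; death combined with disability |

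None of these is a separate early mortality comparison. Even at 3 years no stand-alone test of deaths after 24 hours is specified.

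**2. Does the interim death test use the 24-hour cut?** Section 9.1 does not refer back to 4.1.2, so this is an inference. It is the likely reading, because the plan has no other definition of offspring death.

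**3. Is the plan's own sample size affected?** No. It rests on the 3-year outcome: odds 0.08/0.92 × 2.29 = 0.199, so the control rate is 0.199/1.199 = 16.6%. The two-proportion formula with continuity correction then gives 251 per arm, or 502 against the stated 500. Dropout gives 500/0.75 = 667 against the stated 672. The plan gives no mortality rate or timing of its own to reproduce.

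**4. Illustration for the death test alone.** Assumptions, none of them from the documents: true death rates to discharge of 4% (control) and 10% (pessary), a share *f* of deaths inside the window that is equal in both arms, and twins treated as independent. From the documents: one-sided 1% (critical value 2.326). The interim count can be read as 300 children (150 per arm) or 300 twin pregnancies (300 children per arm).

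With p_C = 0.04*f*, p_T = 0.10*f* and p̄ their mean,

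power ≈ Φ{[(p_T − p_C) − 2.326·√(2p̄(1−p̄)/n)] / √[(p_C(1−p_C) + p_T(1−p_T))/n]}.

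- n = 150, *f* = 1: (0.06 − 2.326 × 0.02946)/0.02926 = −0.29, power about 0.385.
- n = 150, *f* = 0.6: rates 2.4% and 6%; (0.036 − 2.326 × 0.02316)/0.02307 = −0.78, power about 0.22.

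Exact binomial enumeration of the same pooled test, which is safer for small counts, gives:

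| Share of deaths counted | Expected deaths, 150 per arm (control / pessary) | Power, 150 per arm | Power, 300 per arm |
|---|---|---|---|
| 100% | 6 / 15 | 37.9% | 72.5% |
| 90% | 5.4 / 13.5 | 33.7% | 67.0% |
| 80% | 4.8 / 12 | 29.7% | 60.6% |
| 60% | 3.6 / 9 | 22.0% | 45.5% |
| 30% | 1.8 / 4.5 | 7.8% | 22.2% |

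**5. Other assumed rates (normal approximation).** With 100% against 50% of deaths counted:

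| True rates (control / pessary) | 150 per arm | 300 per arm |
|---|---|---|
| 5% / 10% | 25% → 12% | 50% → 24% |
| 3% / 6% | 14% → 7% | 29% → 14% |
| 5% / 15% | 72% → 37% | 96% → 69% |

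Counting half the deaths roughly halves the power in most of these cases.

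**The case against.** A reader might infer that harm through later deaths cannot trigger the interim rule at all. The documents do not support that. An infant who dies of sepsis or necrotising enterocolitis in hospital can be an event in the morbidity test, which is itself a binding interim test. Preterm birth, time to birth and birth weight are tested too, and deaths caused by prematurity would be expected to move them. This part of the objection stands, with one limit: some morbidity items need time to be met. An infant who dies on day 2 cannot have been ventilated for more than 72 hours.

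A reader might also take it as settled that the interim uses the 24-hour window. The text says only that death is tested; it could mean any death known at the look. This stands as a caveat, but an endpoint with no stated window in a binding stopping rule needs the same clarification.

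The share of deaths counted may be high. Women are randomised from 16 weeks, so all intrauterine deaths, and first-day deaths after very early delivery, fall inside the window. At 80% to 90% counted the loss is modest. Even with every death counted, power at 150 per arm is only 38%, so the size of the look limits this test as well. Treating twins as independent probably flatters all these figures.

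Finally, later deaths are not lost to the trial: they enter the 3-year outcome, and fatal events are notified individually. That is true, but neither gives an early comparison of mortality between arms.

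**Conclusion.** The concern holds in a limited form. As written, deaths after the first 24 hours enter no separate between-arm mortality comparison before the 3-year composite. The interim death test probably shares this gap, by inference and not by explicit statement. The loss is to that one test and to the secondary mortality result, not to the interim rule as a whole.

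Its size cannot be fixed from the documents. On the assumed 4% against 10%, it runs from about 4 percentage points of power (150 per arm, 90% counted) to about 50 points (300 per arm, 30% counted). These figures are illustrative and describe a single test. The sample size of 500 evaluable and 672 recruited is unaffected. The change is worth making because it is cheap and the trial's objective is survival.

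**What to change.** 1. In 4.1.2, define the outcome as intrauterine death, or neonatal death up to 28 completed days or hospital discharge, whichever is later. Keep the 24-hour figure as a descriptive sub-item.
2. In 9.1, state that neonatal death at the interim uses this definition, and that infants still in hospital at the interim data cut are counted by their status at that cut, so that the safety look is not held up.
3. In 9.1, amend the statements that secondary endpoints are analysed directly after the last delivery and followed only to birth. They already conflict with morbidity followed to discharge.

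Cost: changes to protocol and eCRF wording. Infants are already followed to discharge for morbidity, so the only added data item is a vital-status check for those discharged before day 28. The secondary analysis, and to a lesser extent the interim, would wait some weeks longer.
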